couples' relationship distress, and functional impairment than the PFE control. A non-inferiority trial comparing CBCT-OB to CBCT-HB was ruled out because there is insufficient research at this time to establish CBCT's superiority over a control/placebo condition, which is a necessary step for establishing an acceptable non-inferiority margin (i.e., delta). Results of this study will guide future CBCT non-inferiority studies (Stage 3 analysis in Figure 1) by formally testing the superiority of CBCT to a control, and by providing an estimate of the observed difference between CBCT delivery modalities ($\Delta 3$). A tertiary hypothesis predicts that therapy process outcomes such as enrollment and drop-out, therapeutic alliance, and treatment satisfaction will be significantly higher in CBCT-HB compared to the two office-based conditions.

Design strategy and algorithm for pairwise treatment comparisons (see Figure 1):

The primary pairwise comparisons for the 3-arm study are comparing each CBCT delivery modality with the control condition: CBCT-OB vs. PFE control and CBCT-HB vs. PFE control (Stage 1). These comparisons are considered primary in the sense that establishing superiority of each modality to control is necessary before evaluation of each modality's relationship to each other. Specifically, progression to Stage 2 testing (comparison of the two delivery modalities) will occur only if it is found in primary analyses that both modalities are superior to control; progression to Stage 3 (a fully powered non-inferiority trial, not part of the current proposal) occurs only if no statistically significant differences are found for Stage 2.

Figure 1. Study Design Diagram and Hypothesis Testing Algorithm

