unable to attend an assessment appointment in person, the assessment(s) were offered over the phone. The mid-treatment assessment (between sessions 4 and 5) consisted of self-report questionnaires that the participants completed prior to their mid-treatment therapy session. Both members of the couple completed a baseline assessment interview designed to gather background information and to screen for psychiatric disorders. The PTSD-positive Veteran completed an additional baseline interview to assess PTSD symptoms and DSM-5 diagnosis via the CAPS-5. Participants were advised that each assessment meeting was approximately 2-3 hours in length. Informed consent for each participant was performed by study staff. All diagnostic assessment procedures were performed by the Independent Evaluator (IE) who is trained to administer the CAPS-5 to fidelity via practice interviews until a minimum interrater reliability rating of 90% is achieved. CAPS-5 fidelity was monitored in an ongoing fashion to prevent drift (see Assessment and Treatment Fidelity Monitoring). Study staff (e.g., IE, research assistants) administered self-report questionnaires to the partner and discussed with the IE about inclusion/exclusion criteria. Study staff alerted the therapist if either member of the couple showed a marked worsening of symptoms (e.g., suicidal ideation) or a score of a 2 or higher on item 9 of the BDI-II at any assessment occasion. To minimize the risk of bias, the IE stayed blinded to participants' study condition throughout the study.

Randomization Procedures: Eligible couples were randomly assigned 1:1:1 to receive CBCT-HB, CBCT-OB, or PFE using a permuted block randomization scheme using an excel file, which required confirmation of eligibility criteria before treatment assignment

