Study Title: An Integrative Technology Approach to Home-based
Conjoint Therapy for PTSD

Study Identifier: NCT02720016

Document Date: 9/28/21

Statistical Analysis Plan

Analytic Considerations:

a) Analysis sets. The primary analyses use the ITT sample, which consists of all participants who were randomized. Couples that terminated treatment early were invited to complete follow-up assessments and their data were included in the ITT analyses.

b) Treatment of missing data. Missing data were imputed using multiple imputation procedures in the Blimp software, which uses fully Bayesian model-based specification. In order to explore potential reasons for data missingness, dichotomous treatment status (i.e., non-completion versus completion) was modeled using logistic regression and all subject-level characteristics predicting the retention outcome were included as auxiliary variables in the imputation model.

c) Adjustment for multiple outcomes. To address possible Type I errors due to multiple dependent variables, we specified a priori the primary measures corresponding to the stated a priori hypotheses within the following specified domains: PTSD symptoms, relationship satisfaction and functional impairment. For secondary analyses using additional outcome variables within a given domain, we will report both unadjusted p-values and adjusted p-values using a Tukey-type correction for multiple outcomes. Secondary outcomes and exploratory analyses will be evaluated qualitatively in terms of consistency with primary results and conservatively in terms of statistical significance of results. Sensitivity of study results to adjustment for multiplicity of outcomes will be evaluated.

Preliminary Analyses: All statistical procedures were conducted using SPSS and R software programs. Preliminary analyses examined distributional characteristics of study variables to provide a description of the study sample and to allow for assessment of randomization. Demographic, baseline clinical characteristics of the individual Veteran and/or couple dyad, and other putative prognostic variables (e.g., relationship characteristics) were compared for imbalance across the treatment groups using analysis of variance for continuous variables and chi-square tests for categorical variables. Where, despite randomization, significant group differences at baseline were identified, those variables were included as covariates in sensitivity analyses.

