Data reliability checks. Reliability and data reduction issues were addressed using descriptive and inferential statistics. Tests of scale reliability will use the Internal Consistency Method and Cronbach's alpha will be calculated. Cronbach's alpha of 0.80 or greater will be considered evidence of sufficient instrument reliability. As described in Assessment and Treatment Fidelity Monitoring, CAPS reliability will be examined via inter-rater agreement.

Analyses for Efficacy Outcomes (Aim 1):

Statistical approach. Longitudinal trajectories of outcomes from baseline to mid-treatment, post-treatment, 3-month, and 6-month follow-up time points were compared using multivariate, multilevel GLMM, which accommodates a wide range of distributional assumptions, including continuous (e.g., CAPS scores, PCL, CSI, IPF, BDI-II, STAXI), categorical/dichotomous (e.g., diagnostic status, treatment completion), ordinal, and count predictors. For outcomes including both members of dyads (e.g., relationship

[figure not shown]
satisfaction), GLMM allowed for modeling multilevel data, as well as for testing other possible cluster effects due to correlation between participants within therapists through inclusion of random effects in the model.

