Model construction. The primary efficacy outcome variables are (1) Veteran-reported PTSD symptom reduction (CAPS severity scores), (2) Veteran- and partner-reported relationship distress (CSI) and (3) Veteran-reported functional impairment (IPF). Secondary variables include PTSD diagnostic status (CAPS), self- reported PTSD symptoms (PCL), depression scores (BDI-II), anger (STAXI-2), and relationship conflict (CTS-2). Variability in scores for each of the primary and secondary outcome measures were examined individually in a series of separate multilevel models. Piecewise/spline models were used to estimate separate slopes for the treatment period and the follow-up period. Each model examined the predictive value of the primary variable of interest: (1) two time slopes (treatment and follow-up; fixed effects), (2) treatment group (fixed effects), and (3) the cross-level interactions of time*treatment group (fixed effects). Baseline scores on the dependent measure were also included as a model covariate, to control for their effect. For couple-based outcomes (e.g., CSI scores), between-dyad, within-dyad, and mixed variables were coded in the model as described by Campbell and Kashy, 2002. As preliminary analyses indicated an imbalance both relationship length and partner-reported CSI scores between treatment groups, subsequent sensitivity models were conducted to control for their effects. For Stage 1 analyses (Aim 1a), pairwise unadjusted and covariate-adjusted differences in least squares means for each outcome variable were compared at mid-treatment, post-treatment, and at the 3- and 6-month follow-up time points using appropriate model

contrasts (i.e., CBCT-OB vs. PFE and CBCT-HB vs. PFE). Next, in Stage 2 analyses (Aim 1b), unadjusted and least squares adjusted means from the GLMM contrast comparisons, along with corresponding 95% CIs, provided estimates of the magnitude (effect sizes), direction, and statistical significance of differences in outcome measures for CBCT-OB compared to CBCT-HB. Progression to a fully powered non-inferiority trial (Stage 3, Figure 1) was determined to occur only if both CBCT delivery modalities are superior to the control intervention (Aim 1a and b). This study provides necessary input information (e.g., variance-covariance and effect size estimates) for the design of the subsequent non-inferiority study.

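### The Aim 1 efficacy model appears to use the baseline score both as an outcome row and as a covariate, with no stated participant-level covariance; with only a random intercept the visit-wise Stage 1 standard errors would be mis-stated

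*SAP*

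**What the plan says.** Under Statistical approach, the SAP says "Longitudinal trajectories of outcomes from baseline to mid-treatment, post-treatment, 3-month, and 6-month follow-up time points were compared", so baseline is the first point of the modelled curve. Model construction adds "Piecewise/spline models were used to estimate separate slopes for the treatment period and the follow-up period" and then "Baseline scores on the dependent measure were also included as a model covariate, to control for their effect". Neither section says that the baseline row leaves the outcome vector.

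The time slopes, treatment group and their interactions are labelled fixed effects. Random effects are mentioned for dyadic data and for "testing other possible cluster effects due to correlation between participants within therapists through inclusion of random effects in the model". The models are called multilevel, but no participant random intercept, random slope, residual structure or robust standard error is named.

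Stage 1 rests on "pairwise unadjusted and covariate-adjusted differences in least squares means for each outcome variable" at mid-treatment, post-treatment, 3 and 6 months. Under the protocol's design strategy, Stage 2 testing "will occur only if it is found in primary analyses that both modalities are superior to control".

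**The concern.** A baseline row that is also its own covariate is predicted perfectly by that covariate, yet the model gives it the same coefficient and residual variance as the follow-up rows. That distorts the estimated split between and within participants, on which the standard error of a visit-wise contrast depends.

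For CAPS the double use is hard to avoid. The protocol says "The mid-treatment assessment (between sessions 4 and 5) consisted of self-report questionnaires", while CAPS-5 is an interview by an independent evaluator. Without the baseline row, only the post-treatment CAPS value falls in the treatment period, and the stated slope could not be estimated. For CSI and IPF, a mid-treatment value could support a slope without baseline.

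At stake are the tests that decide whether each CBCT modality beats PFE, and hence whether the modalities are compared with each other.

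**Working it through.** The documents give no standard error, SD or correlation, so there is no figure to reproduce.

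**Inputs.** From the documents: 137 couples randomised 1:1:1 (taken as 46/46/45); four CAPS visits, five for self-report measures; two piecewise slopes. Assumed: SD 1, visits at months 0, (1), 2, 5 and 8, two-sided 5% (z = 1.96), complete data, no true effect, constant correlation ρ between visits, and a participant random intercept only.

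**Closed form: CAPS, T = 4, ρ = 0.5, 3 months.**

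1. The covariate is constant over a participant's rows, so its coefficient comes from regressing the participant's mean on baseline, and that mean contains baseline: β = [1 + (T−1)ρ]/T = 2.5/4 = 0.625. With post-baseline rows only it would be ρ = 0.5.
2. After removing β × baseline, the baseline row retains 1 − 0.625 = 0.375 of the baseline score and each follow-up row 0.5 − 0.625 = −0.125. The covariance is 0.375 × (−0.125) = −0.047 for the three baseline–follow-up pairs, and ρ − ρ² + 0.125² = 0.266 for the three follow-up pairs.
3. The random-intercept variance is the average over pairs, (−0.047 + 0.266)/2 = 0.109. With covariate-only use it is ρ − ρ² = 0.25.
4. The mean row variance is [0.375² + 3 × (0.75 + 0.0156)]/4 = 0.609, so the residual variance is 0.609 − 0.109 = 0.500.
5. The fitted value at 3 months has leverage h = 1/3 (midpoint of a line through three equally spaced visits). Model variance: 0.109 + 0.500/3 = 0.276. True variance: ρ + (1−ρ)h − 2βρ + β² = 0.500 + 0.167 − 0.625 + 0.391 = 0.432.
6. The SE ratio is √(0.276/0.432) = 0.80, so the error rate is 2Φ(−1.96 × 0.80) ≈ 11.7%. With 1/46 + 1/45 = 0.044, the reported SE is √(0.044 × 0.276) = 0.110 SD against a true √(0.044 × 0.432) = 0.138 SD. The ratio does not depend on sample size.
7. Covariate-only use: the model gives 0.25 + 0.500/3 = 0.417, and the truth is 0.667 − 0.50 + 0.25 = 0.417. The test is correct.

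**Simulation (REML, 10,000 runs per correlation, ρ = 0.4 to 0.8), two-sided error per contrast:**

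| Visit | Four visits (CAPS) | Five visits |
|---|---|---|
| Mid-treatment | – | 1.9–2.1% |
| Post-treatment | 8.4–9.4% | 9.9–10.6% |
| 3 months | 11.6–12.2% | 11.2–11.6% |
| 6 months | 8.4–9.2% | 7.2–7.9% |

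Standard errors are 8–21% too small after treatment and 17–21% too large at mid-treatment. Baseline used once gives 4.7–5.5% (outcome row only) or 4.8–5.4% (covariate only).

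**Extensions at within-person correlation 0.6, random intercepts only.**
- Dyadic CSI (cross-partner correlation 0.3): 2.5, 10.2, 10.9 and 8.1% at mid, post, 3 and 6 months, against 4.7–5.7% with single use.
- The SAP says "Missing data were imputed using multiple imputation procedures in the Blimp software". Imputation does not remove the effect: with 30% missing by 6 months, the 3-month error is 9.1% (four visits) and 10.9% (five), against 4.8–6.1% with single use.

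**Dependence on the covariance, baseline still used twice.**
- Both piecewise slopes random: 3.7–6.0% in a set with mostly 1,600 runs per setting, and about 2.5–6.3% in a smaller set of 300, including decaying correlation. The Monte Carlo standard error at 300 runs is √(0.05 × 0.95/300) = 1.3 points.
- Cluster-robust SE: ratio to the true SD 0.94–1.03.
- Random treatment-period slope only: 4.7–7.2% at constant correlation 0.6, but 15.1–15.5% at 6 months when correlation decays (0.8 per 3 months).
- Random intercept with decaying correlation: 14.1–23.5% at 6 months, but already 9.4–17.7% with covariate-only use, so much of that excess is not due to the double use.

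**What is not affected.** The covariate is constant within a participant and cancels from within-person change. The slope-by-group estimate and SE were the same with and without it (error 5.3%, ρ = 0.5). Point estimates shift by about (β − ρ) × the baseline imbalance: 0.125 × 0.4 = 0.05 SD in the worked case, and 0.02–0.07 SD over the settings tried.

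Therapist clustering, non-random dropout and the exact imputation software were not modelled.

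**The case against.** The SAP nowhere says that only a random intercept was fitted. It describes multilevel models with cross-level time-by-group interactions, and such models often carry participant-level random slopes. With both slopes random, or with robust errors, the double use does almost no harm to Stage 1 error. This stands, and it rules out the stronger reading that a reader might infer: that the trial's Stage 1 standard errors are wrong. But the SAP labels the slopes fixed and names none of these protections, so the fault cannot be excluded either.

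Double use is also inferred. Stage 1 contrasts are listed only at post-baseline visits, which would fit baseline as covariate on post-baseline rows. That is fair for CSI and IPF. It does not work for CAPS with a treatment-period slope, unless CAPS was collected at mid-treatment, which the protocol does not describe.

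A reader might also take the 7 to 12% as the chance of wrongly opening Stage 2. It is not: the rates are two-sided and per contrast. With neither arm effective (random intercept, constant correlation 0.6), both contrasts favoured CBCT in only 0.8–2.0% of 400 runs from post-treatment on. The rate would be higher if one arm truly works.

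Finally, the *unadjusted* contrasts may omit the baseline covariate and so escape the problem. The SAP does not say so, nor that they decide Stage 1.

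**Conclusion.** The concern holds in conditional form. The text supports double use of baseline, all but forced for CAPS, and leaves the participant-level covariance unstated. If that covariance is a random intercept alone, the visit-wise Stage 1 tests are too liberal from post-treatment on (about 7–12% per contrast against a nominal 5%) and too conservative at mid-treatment (about 2%). These figures rest on assumed constant correlation of 0.4–0.8, complete data and no true effect. With both slopes random or a robust SE the error is close to nominal, so the documents establish neither that the reported standard errors were wrong nor that any Stage 1 result is a false positive. The prespecified slope-by-group test is sound on this point.

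**What to change.** Give baseline one role and re-run the Stage 1 contrasts:

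- **(a)** Keep baseline as an outcome row, delete the baseline covariate, and constrain the baseline mean to be common across arms. The piecewise slopes are kept. The common mean matters because the SAP reports an imbalance in partner CSI: without it, 0.17–0.32 SD of a 0.4 SD imbalance stays in the contrasts (correlation 0.5–0.7), against under 0.01 SD with it (correlation 0.6).
- **(b)** Keep the covariate and model post-baseline rows only. This loses the CAPS treatment-period slope.

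With either, state the outcome rows and fit a participant-level covariance richer than a random intercept: unstructured, or both slopes random where estimable. Single covariate use with a random intercept is itself miscalibrated when correlation decays. With an unstructured covariance and decay of 0.8 per 3 months, error was 5.2–6.3% under (a) and 4.7–5.3% under (b). An unstructured covariance should not be added while baseline keeps both roles: a baseline coefficient of 1 makes the baseline residual variance zero and the likelihood degenerate (an analytic point, not simulated).

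As secondary clarifications, say what the *unadjusted* contrasts omit and which set decides Stage 1.

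The cost is a short SAP change, a re-run on existing data and a few more covariance parameters.

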Description of the CBCT Intervention: CBCT is a manualized couple-based intervention for PTSD designed to simultaneously reduce PTSD and enhance relationship functioning. The therapy consists of eight 75-minute sessions organized into two phases that build upon each other and includes both in-and out-of-session exercises to increase skill acquisition. **Phase 1** (Sessions 1–2) focuses on the rationale for the therapy and establishing safety within the relationship (e.g., recognizing early warning signs of anger, use of conflict management strategies). **Phase 2** (Sessions 3–7) focuses on increasing relational satisfaction and undermining PTSD-related distress. The ways avoidance can generalize beyond specific trauma memories and the role of avoidance in maintaining both PTSD and relationship problems are addressed. Couples develop a list of people, places, situations, and feelings that they have avoided as a result of PTSD and begin in vivo exposure exercises to approach these situations in a graduated manner. Special attention is paid to the selection of in vivo approach activities that will address behavioral and experiential avoidance, and concurrently double as shared rewarding activities for the couple. Enhanced dyadic communication is used as an antidote to PTSD-related emotional numbing and avoidance, as well as a means of increasing emotional intimacy. **Final Session** (Session 8) culminates with a discussion of the potential for consolidating newly acquired skills and a review of gains made and challenges expected in the future.

Description of PTSD Family Education (PFE) Control: PTSD Family Education (PFE) consists of eight 60-minute couples' sessions adapted from the Support and Family Education (SAFE) program and the Behavioral Family Therapy (BFT) program.

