is revealed. The randomization schedule was developed and monitored by [name], the study biostatistician, and randomization was communicated to the Veteran by a study approved RA. Study therapists provided care in all conditions. When multiple therapists were available to provide care for the eligible couple, randomization was carried out separately for each therapist, using blocks of decreasing sizes to maintain an approximate balance in the sample sizes for the three arms. However, if a client was recruited from the Oceanside area, placement with an Oceanside therapist was given priority. Only [name], [name] (study statistician), clients and therapists were aware of condition assignment. Once a couple was randomized, they were entered into the study and were included in the ITT analysis. We took the following steps to minimize contamination between the three arms of the study: (1) couples were instructed not to share intervention materials with family members, friends, or other clinic patients; (2) treating VA providers were informed of their patients' participation in the study, but not their condition; and (3) couples were asked not to disclose their treatment assignment to any other counselors or treating physicians.

Treatment Delivery Modality: CBCT-OB and PFE were delivered in the traditional office-based (OB) format - that is, the PTSD-positive participant, his/her partner, and the therapist met in-person in the therapist's office. OB visits took place at two facilities: (1) the Veterans Medical Research Foundation/HSR&D (VMRF/HSR&D) building in La Jolla, CA and (2) 28 miles from La Jolla at the VA clinic in Oceanside, CA. CBCT-HB Couples randomized to the CBCT-HB condition must have had access to DSL or cable internet service or were provided with a VA tablet installed with Wi-Fi through the VA

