Primary Analyses for Process Outcomes (Aim 2): Measures of treatment process outcomes include treatment satisfaction (as measured by the CSQ), therapeutic alliance (for both participants' and therapists' WAI), safety issues (tracked by clinical team) and general program management issues tracked by the coordinator. Additional measures of feasibility are recruitment (percentage who agree to participate out of number approached), compliance (percentage of session attended, percentage of homework assignments completed), and retention (dropout rate). The GLMM framework (with appropriate link functions for dichotomous, ordinal, categorical, and continuous feasibility outcomes) was used to compare the feasibility outcomes between each of the three treatment conditions at the post-treatment time point.

Figure 1. Study Design Diagram and Hypothesis Testing Algorithm

Reference

Campbell, L., & Kashy, D. A. (2002). Estimating actor, partner, and interaction effects for dyadic data using PROC MIXED and HLM: A user-friendly guide. *Personal Relationships*, 9(3), 327-342. doi: 10.1111/1475-6811.00023

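### Safety events are compared between arms at post-treatment at most, from an undefined source, and no event count by arm covers the six months of follow-up

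*SAP*

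**What the plan says.** The SAP section on process outcomes (Aim 2) includes "safety issues (tracked by clinical team) and general program management issues tracked by the coordinator" among its measures. It then says that the GLMM framework "was used to compare the feasibility outcomes between each of the three treatment conditions at the post-treatment time point". Neither document defines a safety issue, says how one is elicited, gives a collection window, or says who belongs to the clinical team.

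Four other places bear on this:

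- **Alert rule.** Protocol, Assessment Administration: study staff alert the therapist if either member of the couple shows marked worsening or "a score of a 2 or higher on item 9 of the BDI-II at any assessment occasion". Assessments run to 6 months after treatment, and the Independent Evaluator is blinded.
- **Who knows the arm.** Protocol, Randomization Procedures: apart from two study roles, "clients and therapists were aware of condition assignment". Therapists work in all three arms.
- **Follow-up of couples who stop.** SAP, Analysis sets: "Couples that terminated treatment early were invited to complete follow-up assessments".
- **Related scales.** SAP, Model construction: BDI-II, STAXI-2 and CTS-2 are secondary outcomes. Least squares means are contrasted between each CBCT arm and PFE at mid-treatment, post-treatment, 3 months and 6 months.

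**The concern.** The trial brings conjoint trauma therapy into the home. The protocol treats suicidality and partner violence as events in their own right: it excludes imminent suicidality and severe aggression at entry, provides for a collateral chart when such a concern arises, and sets an alert on one BDI-II item. Yet no planned analysis counts these events by arm after the end of treatment.

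The source of the safety data is also left open. If the clinical team means the therapists, the people recording safety issues know the arm and see the couples for different lengths of time and with different session content. A reader could not then tell whether a difference, or its absence, reflects harm or ascertainment.

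At stake is whether the report can say anything about the safety of home delivery beyond the last session.

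**Working it through.** The documents give no safety rate and no power calculation for safety, so there is no planned figure to reproduce. The check is mainly of the text, with some side arithmetic.

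**1. Is safety in the post-treatment comparison?** The SAP compares the feasibility outcomes. Its list of process measures, which includes safety issues, is followed by a sentence on additional measures of feasibility, which suggests that the earlier list counts as feasibility too. On that reading there is one safety comparison, at post-treatment. On the other reading there is none. Neither reading covers 3 or 6 months.

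**2. What is left out?** Tracked issues may accumulate over the whole treatment period, as sessions attended and dropout do, so the firm omission is the follow-up period. Treatment length in weeks is not stated. With an assumed length of w weeks and 26 weeks of follow-up, the omitted share is 26/(w + 26):

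| w (assumed) | Share after post-treatment |
|---|---|
| 8 | 26/34 = 76% |
| 12 | 26/38 = 68% |
| 16 | 26/42 = 62% |

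**3. Do the scale means fill the gap?** Only in part. With 137/3, about 46 couples per arm, suppose for illustration that 3 Veterans in an arm move from 0 to 2 on item 9 and nothing else changes. Taking the BDI-II total as the sum of its items, the arm mean rises by 3 × 2/46 = 0.13 points. A count would show 3/46 = 6.5%.

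**4. Is home versus office covered at follow-up?** The Stage 1 contrasts are each CBCT arm against PFE. Under the protocol's Study Design Overview, the two CBCT arms are compared (Stage 2) only if both beat control. If that condition fails, no home-versus-office contrast at 3 or 6 months remains, even on means. The Aim 2 comparison covers all three arms, but only at post-treatment.

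**5. Could detection differ by arm?** For CBCT, "The therapy consists of eight 75-minute sessions": 8 × 75 = 600 minutes. For the control, "PTSD Family Education (PFE) consists of eight 60-minute" couples' sessions: 8 × 60 = 480 minutes. The ratio is 600/480 = 1.25. CBCT opens with sessions on safety in the relationship, whereas PFE clinicians are trained to stay within psychoeducation. This shows opportunity only. If detection did scale fully with minutes, rates of 5%, 10% and 20% (assumed) would appear as 6.25%, 12.5% and 25% in CBCT. At about 46 per arm and two-sided 0.05 (assumed), the chance of a significant difference would be 4%, 6% and 8%.

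**6. What precision would a count have?** Zero events in 46 couples gives a one-sided 95% upper bound of 1 − 0.05^(1/46) = 6.3%, and a two-sided exact 95% upper limit of 1 − 0.025^(1/46) = 7.7%. Power against assumed true rates is low: 36% for 5% vs 15%, 58% for 5% vs 20%, 67% for 10% vs 30%. The zero-event bound depends only on the number of couples, so it describes the precision of a table and does not measure the cost of omitting follow-up.

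**The case against.** The strongest reply is that harm during follow-up is compared. Depression, anger, relationship conflict and PTSD symptoms are contrasted with PFE at 3 and 6 months, and the models include a follow-up slope. This stands against any claim that follow-up harm goes uncompared. It does not answer the point about events, because these are mean scores and the CBCT arms are compared with each other only conditionally.

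A second reply is that the alert rule applies equally in every arm, at every assessment, and reaches couples who stopped treatment if they attend. That also stands, so the documents do not show that couples who stop early are lost to safety detection. But the rule only notifies the therapist; nothing says that alerts are logged or analysed.

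A third reply concerns detection. A reader might infer from the contact minutes that safety issues will be over-counted in CBCT by a factor of 1.25. The documents do not support this. Nothing ties detection to minutes, both interventions have eight sessions, the same therapists work in all arms, and the clinical team is undefined. The projected 20–30% attrition is one overall figure, with no difference between arms. For home versus office, the contact minutes are the same.

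**Conclusion.** The concern holds in a limited form. For safety issues as the SAP names them, the only comparison described is at post-treatment, the source and window are undefined, and no event count by arm covers the six months of follow-up. If treatment lasts 8 to 16 weeks, that is 62% to 76% of observation time.

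It is probable, not stated, that the clinical team includes therapists who know the assignment. Differential detection is possible; neither its presence nor its direction can be read from the documents. A reader might go further and conclude that follow-up harm is ignored or that the safety data are biased against CBCT. The planned contrasts at 3 and 6 months rule out the first, and the second is conjecture.

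This is an inexpensive improvement to harms reporting. It does not threaten the primary efficacy analysis.

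**What to change.** In the Aim 2 section of the SAP, add one table by arm, covering all randomised couples from randomisation to 6 months:

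- **Events.** The number and proportion of couples with a BDI-II item 9 score of 2 or more in either member (the protocol's own alert level), and the number and proportion with severe aggression items endorsed on the CTS-2. Give exact 95% confidence intervals.
- **Periods.** Show treatment and follow-up separately. State the CTS-2 recall period, since a long recall could place an event in the wrong period.
- **Baseline.** Separate events new since baseline from those already present. Entry criteria exclude imminent suicidality but do not expressly exclude an item 9 score of 2.
- **Denominators.** Give the number randomised and the number assessed at each occasion.
- **Alerts.** Include marked-worsening alerts only if they were logged, because no threshold is stated.

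Keep the clinician-tracked issues as a descriptive listing by arm. State who recorded them and over what period, and note that detection may differ by arm. The questionnaires ask every arm the same questions on the same occasions, but couples know their assignment, so this makes elicitation uniform without making reporting blind.

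The cost is some SAP wording and one table from instruments already given, assuming that item-level responses were kept and that the CTS-2 form used at follow-up carries the severe items. The downside is few events, wide intervals and missing follow-up assessments, so the table should be used for estimation and not for testing.
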